Study Protocol

PD-1 Inhibitor Combined With Azacytidine and Homoharringtonine, Cytarabine, G-CSF for Refractory or Relapsed AML

Vision 1.0

Dec. 20, 2020

ClinicalTrials.gov Identifier:

Principal Investigator

[name], PhD, [contact]; [name], PhD,
[contact]. Jiangsu Institute of Hematology, The First Affiliated
Hospital of Soochow University, Suzhou 215006, China.

Protocol version	Issue date
Vision 1.0	Dec. 20, 2020

Vision 1.0 (Dec. 20, 2020)

Applicable Section

Study center:
 
The First Affiliated Hospital of Soochow University, Suzhou 215006, China;

Protocol Summary

Study center
 
 The First Affiliated Hospital of Soochow University, Suzhou 215006, China;

Principal Investigator
 
[name], PhD; [name], PhD.

Methodology
 
A prospective, single-arm, single-center, randomized clinical trial.

Primary objective
 
To assess the efficacy and safety of PD-1 inhibitor combined with azacytidine and homoharringtonine, cytarabine, G-CSF for refractory or relapsed AML .

Inclusion criteria
 
 Chinese guidelines for the diagnosis and treatment of relapsed and refractory acute myeloid leukemia (2017 edition), excludes acute promyelocytic leukemia (M3、APL); Hematopoietic stem cell transplantation ≥ 3 months, Discontinue immunosuppressant ≥ 3 weeks, Patients without graft-versus-host disease; Be at least 18 years of age on day of signing informed consent; Have a performance status of less than or equal to 2 on the Eastern Cooperative Oncology Group (ECOG) Performance Scale; Demonstrate adequate organ function as defined below, all screening labs should be performed before treatment initiation: 
 ALT(SGPT) less than or equal to $2.5 \times$ Upper Limit of Norma (ULN) ; AST (SGOT) less than or equal to $2.5 \times$ ULN;

3. Serum total bilirubin Less than or equal to 2.0 × ULN; Note: If total bilirubin >2.0×ULN, subjects with Gilbert syndrome records are allowed to join the group;
 
4. Serum Creatinine ≥ 30 mL/min
 
5. Total white blood cell (WBC) count ≤10,000/μL; Note: hydroxyurea therapy is allowed to reduce white blood cells to meet this inclusion criteria. white blood cells should be determined ≥24 hours after the last hydroxyurea administration. Final hydroxyurea administration should not ≤3 days prior to the first azacytidine administration.


Exclusion criteria
 
 • Patients with chronic myeloid leukemia, AML of other myeloproliferative disorders Malignant neoplasms with other progression ; • Those who can not control severe infections and other underlying diseases can not tolerate chemotherapy ; • Patients with cardiac insufficiency: ejection fraction (EF)<30%, New York Heart Association (NYHA) standards, Cardiac insufficiency II or above; • Patients with liver and kidney dysfunction: Serum bilirubin (SB)≥2mg/dl, AST is 2.5 times higher than normal upper limit, serum creatinine (SCr) is more than 2.5 mg/dl Serious mental illness uncooperative Refusal to join the study;

Intervention
 
 • Azacytidine 75mg/(m².d) by IV on days 1-7 of every cycle. • Anti-PD-1 mAb 200mg by IV on day 8 of every cycle. • Homoharringtonine(HHT) 2mg/(m².d) by IV on days 1-6 of every cycle Cytarabine 10mg/(m².d) by SC on days 1-7 of every cycle Granulocyte colony-stimulating factor(G-CSF) 300ug/d by SC on days 1-7 of every cycle, until absolute neutrophil count(ANC) > 5X10⁹ / L or white blood cell (WBC) > 20X10⁹ / L.

Total number of patients: 30

Total duration of the study: 3 years

Background

Acute myeloid leukemia (AML) is one of the most common hematological malignancies, a malignant, clonal disease with poor prognosis. The rate of complete remission (CR) was 60%-90% in patients with first induction chemotherapy, 10%~40% became refractory. 70% of AML patients who received the first CR maybe relapsed in the first year after the CR¹. The 5 years total survival (OS) rate of refractory or relapsed AML (RR-AML) was 5%~10%, and the CR rate was not more than 30% in general². There is still no unified treatment regimen for RR-AML, according to Chinese guidelines for diagnosis and treatment (2017 Edition)³ and United States National Integrated Cancer Network (NCCN) 2019 edition AML clinical practice guidelines standard⁴, they still emphasize individualized treatment and salvage chemotherapy. Therefore, how to treat refractory or relapsed acute myeloid leukemia is still an urgent clinical problem.

Many studies have shown that epigenetic changes such as DNA methylation are common in AML and play an important role in the transformation of myelodysplastic syndrome (MDS) to AML. Demethylation drugs have become the first-line treatment of AML drugs. The azacitidine is a 5-azide analogues, which has dual mechanism of demethylation and integrates into DNA and RNA to produce antitumor activity, approved by Europe in 2008 and China in 2018 for treatment of AML with 20%~30% bone marrow blast cells⁵⁻⁶. Chinese guidelines for the diagnosis and treatment of relapsed and refractory acute myeloid leukemia (version 2017)³ recommended demethylation drugs for patients with poor tolerance and unsuitable for strong chemotherapy regimens.

Demethylation drugs have been reported to increase the sensitivity of CAG、HAG and other chemotherapy regimens, thereby improving clinical efficacy⁷⁻⁸. Homoharringtonine is a cell cycle specific alkaloid. There are clinical studies showing that the CR rate of the homoharringtonine combined

with CAG regimen is higher than the CAG regimen for RR-AML⁹. Based on this study, azacytidine combined with HAG regimen was used to treat refractory and relapsed patients.

Ørskov AD¹⁰ found that MDS patients treated with demethylated drugs (HMAs) lead to the demethylation of programmed death receptor 1 (PD-1) promoter in T cells. And then the expression of PD-1 increased in T cell surface, and the combination of tumor cell surface PD-L1 hindered the anti-tumor immune response. Therefore, this immune checkpoint upregulation also provides strong evidence for the use of PD-1 or PD-L1 pathway inhibitors to overcome tumor immune resistance. In a phase II clinical trial, PD-1 inhibitor nivolumab combined with azacytidine treated 70 patients with recurrent AML¹¹, regimen: Azacytidine 75 mg/m², d1-7; nivolumab 3mg/kg, d1, d14; 4-5w treatment. The total response rate was 33%, patients treated with HMAs for the first time was 58%, other patients was 22%. 11% incidence of immune-related side effects at level 3-4. The median overall survival of all patients was 6.3 months, According to the institutional experience of MD Anderson Cancer Center, it has advantages over azacytidine-based chemotherapy.

To improve the prognosis and survival of RR-AML patients, we propose to conduct a prospective study to explore the efficacy and safety of PD-1 inhibitor combined with azacytidine and HAG regimen in the treatment of RR-AML, and to study its related mechanisms.

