Secondary objectives and secondary endpoints:

Number of Participants (Responders) Achieving Overall Response Rate (ORR) After the Eighth Cycle Treatments; time from randomization to death from any cause; The time between the beginning of the group and the occurrence of any event, including death, progression of the disease, chemotherapy regimen, conversion to chemotherapy, addition of other treatment, occurrence of fatal or intolerable side effects, etc; Time between the beginning of randomization and the progression (in any way) of tumorigenesis or (for any reason) death

Research design

Type of study

This is a prospective, single-arm, single-center randomized clinical trial.

Experimental diagram

The overall design of the study is shown in Figure 1.

[figure not shown]

Figure 1. The flow chart of the overall study design

Dosage and administration

Treatment:

Azacytidine 75mg/(m².d) by IV on days 1-7 of every cycle;

PD-1 inhibitor 200mg by IV on day 8 of every cycle;

Homoharringtonine(HHT) 2mg/(m².d) by IV on days 1-6 of every cycle

Cytarabine 10mg/(m².d) by SC on days 1-7 of every cycle

Granulocyte colony-stimulating factor(G-CSF) 300ug/d by SC on days 1-7 of every

cycle , until absolute neutrophil count(ANC) > 5X10⁹ / L or white blood

cell (WBC) > 20X10⁹ / L.

Study process

Screening phase (3 days)

- Inclusion /Exclusion Criteria
- Demographic data: age, sex, nationality, address, spouse's characteristics, contact information.
- Physical examination: height, body weight, blood pressure, body temperature, heart rate, body surface area, respiratory and cardiovascular system examination, nervous system examination, Eastern Cooperative Oncology Group (ECOG) score, etc.
- Laboratory examination:
 - Blood analysis: blood routine test, blood biochemistry
 - BM examination: marrow morphology examination, Flow cytology, etc.

Treatment period (28 days)

- Drugs will be given based on the protocol;
- Blood routine test and blood biochemistry are performed once a day and once a week, respectively;
- T Cellular Subjects and PD-1 are performed before AZA;
- Important vital signs are recorded;
- Adverse events will be recorded and managed according to this protocol.

Termination phase

- Demographic data: age, sex, nationality, address, spouse's characteristics, contact information.
- General information: past history, allergic history, previous disease and status.

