- Definite relevance: The adverse event is clearly related to the investigational agent. For example, an event that follows a reasonable temporal sequence from administration of the study intervention abides by a known or expected response pattern to the suspected intervention, which improves by stoppage and reappears through repeated exposures, but is unable to be reasonably explained by the known characteristics of the subject's clinical state;
- Possible relevance: An adverse event that follows a reasonable temporal sequence from administration of the study intervention abides by a known or expected response pattern to the suspected intervention, which can be easily induced by various other factors;
- Irrelevance: The adverse event is clearly uncorrelated with the research agent or procedure. For example, there exists another plausible cause, and/or a clinically plausible temporal sequence is inconsistent with the onset of the event and the study intervention and/or a causal relationship is considered biologically implausible.

Serious adverse event:

A serious adverse event (SAE) event is defined as the event with one of the following consequences:

- Death;
- Life-threatening condition;
- Hospitalization or extension of hospitalization;
- Temporary or permanent disability;
- Congenital anomaly or malformation;

-
- Important medical events: although the event caused by the drug which may endanger the subjects may not be life-threatening and result in death or require hospitalization, medical or surgical intervention requires to be taken to prevent one of the outcomes based on the appropriate medical judgment.

Definition of an unexpected adverse event:

An unexpected adverse event of the product is defined as the event with the nature, severity or course non-corresponding to the product information mentioned in the summary when it is authorized or in the investigator's brochure when it is not authorized.

Expected adverse events:**➤ Due to myelosuppression**

Neutropenia related infections, fever;

Bleeding: ecchymosis, petechial, haematemesis, hemoptysis, melena, hematuria, etc;

Weary, somnolence, pale, etc (due to anemia);

➤ Due to other non-hematological toxicity

Liver dysfunction;

Renal dysfunction;

➤ Related to the haematological disease

Death

Relapse of any kind

➤ Related to drug allergy

Erythra, edema, pruritus, swelling, etc.

Procedures of all adverse event

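### Pregnant and breast-feeding patients are not excluded and screening has no pregnancy test, so an unrecognised pregnancy can be enrolled as the plan is written

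*Combined protocol and SAP*

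**What the plan says.** The inclusion and exclusion criteria are set out once, in the Protocol Summary. The screening phase under Study process only refers back to them.

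- **Age and sex.** The age criterion is "Be at least 18 years of age on day of signing informed consent". There is no upper limit and no condition on sex or childbearing potential.
- **Exclusions.** Apart from other malignancies, cardiac insufficiency, and liver and kidney dysfunction, the list contains a general item, "Those who can not control severe infections and other underlying diseases can not tolerate chemotherapy", and ends with "Serious mental illness uncooperative Refusal to join the study".
- **Immune status.** The one entry condition that touches it is in the transplant criterion: "Discontinue immunosuppressant ≥ 3 weeks, Patients without graft-versus-host disease".
- **Screening tests.** The laboratory items are "Blood analysis: blood routine test, blood biochemistry" and "BM examination: marrow morphology examination, Flow cytology, etc".
- **Medical history.** Past history, allergies and previous disease are listed under the termination phase. The screening list has no such item.
- **Treatment.** Every cycle includes azacytidine, homoharringtonine, cytarabine, G-CSF and a PD-1 inhibitor.

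Two other places bear on the point. The definition of a serious adverse event includes "Congenital anomaly or malformation". The Background reports, for a cited trial of a PD-1 inhibitor with azacytidine, "11% incidence of immune-related side effects at level 3-4".

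**The concern.** An eligibility list is applied as written. If pregnancy is not named and no test is scheduled, an early pregnancy that neither patient nor physician suspects will not be found before the first dose. The regimen combines three cytotoxic or hypomethylating drugs with an immune checkpoint inhibitor, so this is a question of patient safety first.

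There is also a smaller matter of interpretation. Safety is part of the primary objective. If pre-existing autoimmune disease is not recorded before treatment, a later immune-related event has no documented baseline to be read against. The protocol already treats immune status as relevant to entry after transplantation, but says nothing about autoimmune disease in any patient.

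**Working it through.** The protocol gives no figure to reproduce, and no formula applies. The check is a reading of the whole document for the missing terms and for anything that could stand in for them.

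1. **Search.** The supplied text nowhere mentions pregnancy, breast-feeding, contraception, a pregnancy test or autoimmune disease. The exclusion list is run together by the conversion from PDF, but nothing suggests that items were cut off or blacked out.

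2. **A literal walk through entry.** Take an adult with relapsed AML, ECOG 2 or better, adequate organ function, a qualifying white cell count and an early pregnancy. She meets the inclusion criteria and no exclusion applies to her. The screening blood tests and marrow are done, and none of the named tests looks for pregnancy. She is eligible and can be dosed.

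3. **Clauses that might close the gap.**

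| Clause | Where | Does it cover pregnancy or breast-feeding? |
|---|---|---|
| Underlying disease that cannot tolerate chemotherapy | Exclusion criteria | No. It concerns disease and tolerance. |
| Immunosuppressant stopped, no graft-versus-host disease | Inclusion criteria, transplant item | No |
| Safety laboratory list with virology and ECG | Safety evaluations | Not named. The list is open-ended and not tied to screening. |
| Withdrawal when the protocol proves unsuitable, or in the patient's best interests | Withdrawal from the study | Only after inclusion, and pregnancy is not named |
| Safety committee and ethics committee review | Monitoring committee; Responsibility of independent ethics committee | Oversight of the trial; neither is a per-patient check before dosing |

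4. **The same reading for autoimmune disease.** The transplant condition, even if applied to every patient, would catch recent immunosuppressive treatment but not untreated active disease. The tolerance clause refers to chemotherapy and need not cover a condition relevant to a PD-1 inhibitor. Previous disease is scheduled for collection only at termination, so no explicit step before dosing records it.

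**The case against.** The strongest reply is that the point rests on silence. No two sections contradict each other, and the document does not say that these drugs harm a fetus. Investigators would in practice ask about pregnancy. The consent form, listed as Appendix 3, is not in the supplied text and may carry wording on pregnancy or contraception. For relapsed AML, with the five-year survival of 5% to 10% that the Background quotes, whom to treat is a clinical judgement.

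Part of this stands. The consent form could say more, and whether active autoimmune disease should bar entry is for the sponsor to decide. But consent wording is neither an eligibility criterion nor a scheduled test, and routine questioning does not reliably find a pregnancy that nobody suspects.

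A reader might also infer four stronger things that the document does not support:

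- **That the protocol itself foresees fetal harm.** The congenital-anomaly line belongs to a general definition of seriousness. The trial's own list of expected adverse events names neither fetal harm nor autoimmune flare.
- **That a definite number of patients is at risk.** Multiplying 30 by assumed proportions would count women who could become pregnant, not pregnancies. A general rate of autoimmune disease would likewise not measure active disease. The protocol supplies neither figure.
- **That about three severe immune events are expected.** Applying 11% to 30 patients gives 0.11 × 30 = 3.3, but the 11% comes from nivolumab 3 mg/kg on days 1 and 14 with azacytidine. This trial gives 200 mg of a PD-1 inhibitor on day 8 with azacytidine and HAG, and it makes no such projection.
- **That a flare of old disease could not be told from new toxicity.** The relevance scale provides for the patient's clinical state, for other contributing factors and for another plausible cause. Attribution is harder without a baseline history, but not impossible.

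**Conclusion.** The point holds for pregnancy and breast-feeding. Neither is excluded, no pregnancy test is scheduled at screening, and no other section makes up for this. An adult with an unrecognised pregnancy can be enrolled without any departure from the protocol.

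Its size cannot be stated as a number. All 30 patients pass through the same criteria, but how many could be pregnant depends on an age and sex mix that the protocol does not give. The conclusion rests on two assumptions: that the sponsor does not intend to enrol pregnant or breast-feeding patients, and that the missing consent form does not itself set an entry rule or a test.

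The autoimmune part is secondary. It supports collecting the history before treatment and asking the sponsor for an explicit position. It does not establish that such patients must be excluded. Neither part affects the validity of the response or survival analyses. This is an inexpensive safety improvement that should be made.

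**What to change.** 1. Add pregnancy and breast-feeding to the exclusion criteria in the Protocol Summary.
2. Add to the screening phase a pregnancy test for patients who could be pregnant, run on the blood sample already drawn, with the result available before the first dose.
3. List past history and previous disease, including autoimmune disease, under screening, so that immune-related events can be read against baseline.
4. Have the sponsor state whether patients with active autoimmune disease are eligible. The choice is the sponsor's; the protocol should record it.

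The cost is a few lines of protocol wording, one assay per relevant patient and a short history item. The downside is that a few patients may be screened out. No analysis changes.

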Secondary objectives and secondary endpoints:

Number of Participants (Responders) Achieving Overall Response Rate (ORR) After the Eighth Cycle Treatments; time from randomization to death from any cause; The time between the beginning of the group and the occurrence of any event, including death, progression of the disease, chemotherapy regimen, conversion to chemotherapy, addition of other treatment, occurrence of fatal or intolerable side effects, etc; Time between the beginning of randomization and the progression (in any way) of tumorigenesis or (for any reason) death

Research design

Type of study

This is a prospective, single-arm, single-center randomized clinical trial.

Experimental diagram

The overall design of the study is shown in Figure 1.

[figure not shown]

Figure 1. The flow chart of the overall study design

Dosage and administration

Treatment:

Azacytidine 75mg/(m².d) by IV on days 1-7 of every cycle;

PD-1 inhibitor 200mg by IV on day 8 of every cycle;

Homoharringtonine(HHT) 2mg/(m².d) by IV on days 1-6 of every cycle

Cytarabine 10mg/(m².d) by SC on days 1-7 of every cycle

Granulocyte colony-stimulating factor(G-CSF) 300ug/d by SC on days 1-7 of every

cycle , until absolute neutrophil count(ANC) > 5X10⁹ / L or white blood

cell (WBC) > 20X10⁹ / L.

Study process

Screening phase (3 days)

- Inclusion /Exclusion Criteria
- Demographic data: age, sex, nationality, address, spouse's characteristics, contact information.
- Physical examination: height, body weight, blood pressure, body temperature, heart rate, body surface area, respiratory and cardiovascular system examination, nervous system examination, Eastern Cooperative Oncology Group (ECOG) score, etc.
- Laboratory examination:
 - Blood analysis: blood routine test, blood biochemistry
 - BM examination: marrow morphology examination, Flow cytology, etc.

Treatment period (28 days)

- Drugs will be given based on the protocol;
- Blood routine test and blood biochemistry are performed once a day and once a week, respectively;
- T Cellular Subjects and PD-1 are performed before AZA;
- Important vital signs are recorded;
- Adverse events will be recorded and managed according to this protocol.

Termination phase

- Demographic data: age, sex, nationality, address, spouse's characteristics, contact information.
- General information: past history, allergic history, previous disease and status.

- Physical examination: height, body weight, blood pressure, body temperature, heart rate, body surface area, respiratory and cardiovascular system examination, nervous system examination, ECOG score, etc.
- Laboratory examination:
 - Blood analysis: blood routine test, blood biochemistry,
 - T Cellular Subjects and PD-1 are performed ;
 - Bone marrow examination: marrow morphology examination, flow cytology.

Follow-up phase (6 months)

- Routine blood examination will be repeated once every 1 month;
- The changes of other complications;
- Survival will be long-term recorded until death.

Response evaluation

- Response: According to the 2020 NCCN guidelines.

Safety evaluations

Safety and tolerability are assessed throughout the study.

Safety endpoints

White blood cell count, hemoglobin, liver function, renal function.

Clinical symptoms:

Newly occurred symptoms during the study period: fever, nausea, cough, somnolence, depression, constipation, diarrhea, petechia, edema, pharyngitis, pulmonary edema, atrial fibrillation, tachycardia, mycobacterium avium complex infectious, hyperglycemia, neutropenia, anemia.

Laboratory examination

Blood routine test, blood biochemistry, virological testing, electrocardiogram, etc.

Adverse event**Definition and record of an adverse event**

Adverse events are defined as any harmful medical manifestations occurring in a person who participates in a biomedical research whether this manifestation is related to the research or the product used in the research. An adverse effect may be any unfavourable or unexpected sign (including abnormal laboratory results), any symptom or temporary disorder associated with the use of the product, with or without relation to the product.

The clinically significant abnormality must be reported as an adverse event (AE) in the eCRF, and AE is supposed to record the time of occurrence, the stage of severity, the duration of time, measures and outcomes.

Classification of adverse event severity

Every case report is performed by the grade of severity about drug adverse reactions:

- Mild: usually transient symptoms unaffecting the daily life;

- Moderate: symptoms probably affecting the daily life;
- Severe: symptoms seriously affecting the daily life.

Relevance

- Definite relevance: The adverse event is clearly related to the investigational agent. For example, an event that follows a reasonable temporal sequence from administration of the study intervention abides by a known or expected response pattern to the suspected intervention, which improves by stoppage and reappears through repeated exposures, but is unable to be reasonably explained by the known characteristics of the subject's clinical state;
- Possible relevance: An adverse event that follows a reasonable temporal sequence from administration of the study intervention abides by a known or expected response pattern to the suspected intervention, which can be easily induced by various other factors;
- Irrelevance: The adverse event is clearly uncorrelated with the research agent or procedure. For example, there exists another plausible cause, and/or a clinically plausible temporal sequence is inconsistent with the onset of the event and the study intervention and/or a causal relationship is considered biologically implausible.

Serious adverse event:

A serious adverse event (SAE) event is defined as the event with one of the following consequences:

- Death;
- Life-threatening condition;
- Hospitalization or extension of hospitalization;
- Temporary or permanent disability;
- Congenital anomaly or malformation;

-
- Important medical events: although the event caused by the drug which may endanger the subjects may not be life-threatening and result in death or require hospitalization, medical or surgical intervention requires to be taken to prevent one of the outcomes based on the appropriate medical judgment.

Definition of an unexpected adverse event:

An unexpected adverse event of the product is defined as the event with the nature, severity or course non-corresponding to the product information mentioned in the summary when it is authorized or in the investigator's brochure when it is not authorized.

Expected adverse events:**➤ Due to myelosuppression**

Neutropenia related infections, fever;

Bleeding: ecchymosis, petechial, haematemesis, hemoptysis, melena, hematuria, etc;

Weary, somnolence, pale, etc (due to anemia);

➤ Due to other non-hematological toxicity

Liver dysfunction;

Renal dysfunction;

➤ Related to the haematological disease

Death

Relapse of any kind

➤ Related to drug allergy

Erythra, edema, pruritus, swelling, etc.

Procedures of all adverse event

Investigators must immediately take necessarily measures at once to protect subjects' safety, when serious adverse events occur. Furthermore, all adverse

events should be followed up and investigated, and detailed records are supposed to be made and signed.

All serious and non-serious AEs and special situation will be reported from the signature to completion of the subject's last study-related procedure (which may include the follow-up contact for safety). SAEs must be reported using the Serious Adverse Event Form. The sponsor will evaluate any safety information that is spontaneously reported by an investigator beyond the time frame specified in the protocol.

All AEs, regardless of the severity or presumed relationship with the study treatment, must be recorded in the source document and eCRF using medical terminology. Whenever possible, diagnosis should be made when signs and symptoms are caused by the common etiology. Investigators must record their opinions on the relationship between AEs and the study treatment in the eCRF. All measures required for (serious) AEs must be recorded in the source document and reported according to sponsor instructions.

Monitoring committee

A safety committee comprised of 3 persons independent of the trial will be organized and will meet to check the safety related to the study treatment during the study. In terms of the overall mortality of each arm and serious adverse events, review will be performed by the independent safety committee. The committee is responsible for haemovigilance/pharmacovigilance of the study and acts as an additional warning sign against haemovigilance/pharmacovigilance of the study.

Contact

[name] (Email: [contact]), [name] ([contact]),
The First Affiliated Hospital of Soochow University, Suzhou 215006, China.

Statistical methods

Statistical analysis will be done by the sponsor or under the authority of the sponsor. A general description of the statistical methods to be used to analyze the efficacy and safety data is outlined below. Baseline for all analyses will be the day of randomization unless otherwise specified.

Sample size estimation

We used the formula of sample size estimate when comparing the independent rates two groups.

AZA CR/CRi	PD-1+AZA+HAG CR/CRi	Testing effectiveness
18%	38.5 %	80 %

$\alpha=0.05$, bilateral test

Statistical analysis

Kaplan- Meier method was performed to estimate the 1-year survival rate

Procedures

All initial PQCs must be reported to the sponsor by the investigational staff within 24 hours after being made aware of the event.

If the defect is combined with an SAE, the investigational staff must report the PQC to the sponsor according to the SAE reporting timelines. A sample of the suspected product should be maintained for further investigation if requested by the sponsor.

Ethical statement

Ethical principles

The study should be carried out in accordance with Helsinki declaration proposed by World Medical Association and subsequent amendments and approved by the Independent Ethics Committee (IEC) before implementation.

Information and informed consent

- All the patients who agree to participate should be asked to sign the informed consent form to prove their approval for participation in this study. The informed consent form must be signed and dated personally by the patients and investigators.
- Before obtaining the informed consent, the investigators must provide sufficient information to the patients who are potential participants in this study:
 - The investigators should orally inform the patients of all the relevant circumstances of this study;
 - The information provided to patients must be fully and easily understood by non-professionals, so that they can make a decision according to their own willingness based on their full understanding of this study;
 - Additionally, the patients voluntarily participate in the study, and are free to quit from the study at any time, without any reasons. The subsequent treatment of patients is not under the influence of unwilling to participate or quitting from the study.
- All the patients who agree to participate should be asked to sign the Informed Consent Form (ICF) to prove their approval for participation in this study. The ICF must be signed and dated personally by the patients and the investigators;

-
- The signed ICF will be kept in the Data Center and must be safely kept for future review at any time throughout the study.

Withdrawal from the study

The main withdrawal criteria are as following:

- Changes in the patient's condition after inclusion, which suggests that the study protocol is unsuitable for the patient;
- Severe complications affecting the implementation of the study treatment;
- Patients who are confirmed to require emergency treatment due to other diseases after inclusion;
- Treatment unmated with the study protocol;
- Patients who voluntarily quit or discontinue any examination, treatment and monitoring required by the study for personal reasons at any stage after inclusion in this study. The PI also has the right to withdraw patients from the study if he/she feels that the withdrawal is in the best interests of the patients.

Identity and privacy of patients

- After obtaining an ICF, each enrolled patient is assigned a subject number (allocation number). This number will represent the identity of the patient during the study and for the retrieving of dedicated clinical research database;
- Throughout the study, several measures will be taken to minimize any breaches of personal information, including:
 - Only the PI and co-investigators will be able to link to the research data of the patients to themselves through the identifiable table after authorization;
 - Collection, transmission, handling and storage of the study data must comply with the data protection and privacy regulations.

Responsibility of independent ethics committee

The responsibilities of independent ethics committee include:

- Review of this study;
- Evaluate this study to determine if risks to which patients are exposed have been duly minimized and whether these risks are reasonable compared to expected benefits;
- Check the study protocol and relevant documents (patient information sheet, ICF, CRF, etc.) submitted by the Research Committee before beginning of the study;
- Provide the written proof of ethical review opinions, the written proof of the date of the review meeting, the written proof of the members presenting at the meeting and voting members, the written proof of recording of the reviewed versions of study protocol, ICF and other related documents, and if possible, a copy of the minutes, to the Research Committee. The study can begin only after obtaining the written proof of favorable opinions/approval of the IEC;
- Supervise the legitimacy of the process of informed consent;
- Ensure the safety of patients during the research process by examining the reported safety information. The investigators should report to the IEC on any therapeutic complications which may affect the safety of patients. When complications that affect the patient safety occur, the IEC should inform PI to withdraw patients from the study and use any possible treatment to cure patients. If the PI decides not to withdraw patients from the study, he should provide a written proof of explanation to the IEC;
- Review the reasonableness of the costs incurred by patients in the course of the study through a selective check for hospitalization expenses. When the patient has indications for off-label use of drugs, the IEC will receive the notice and the description of relevant situation from the investigators. The IEC should record the relevant records;

-
- Review the revisions of the study protocol, and any changes must be approved by the IEC before they are adopted. Unless the change is necessary to eliminate an immediate hazard to the patients, in which case the IEC should be informed as soon as possible;
 - Review the progress of the study annually and the close-out report submitted by the Research Committee at the end of the trial.

Responsibility of investigator

The responsibilities of investigators are as follows:

- Investigators, participated in the clinical trial, should be obtained certificate for assistant practicing doctor, resigned and attended the training of the GCP guidelines and the correlation of laws and regulations, possessed specialty, qualification and ability in clinical trial.
- Subjects are adequately recruited by the investigator during required time according to the clinical trial, and operation capacity and possibility to be qualified the item should be evaluated by the previous working experience.
- Investigators are familiar with clinical trial protocols and execute instruction strictly according to the protocols and case report form.
- In all adverse events, subjects must be taken appropriate therapies and made a contact with the investigator as soon as possible. Investigators will take responsibilities of relevant medical decision of clinical trial to ensure subjects that is taken adequate medical treatment.
- Any information on the case report form possesses original data, to ensure the case history and case report form filled in truly, accurately, completely, timely, regularly and legally.
- Subjects will be illustrated the relevant situation where the clinical trial is fully consent by Ethics Committee. The informed consent will be acquired and, during the process, it must meet the specification.

-
- Supervision and inspection will be received by supervisor and inspector assigned by sponsor to ensure the quality of clinical trial.
 - Any advices and suggestions focused on the study protocols might be submit to the principal institution of clinical research, and made a discussion with sponsor and coordination institutions to decide whether adopting the above advice or suggestions, during the clinical trial executed by each institutions.

Publications

- All the data collected during this study are the property of the study sponsor and cannot be communicated in any case to a third party without the written agreement of the investigator.
- Any publication or communication (oral or written) will be decided from a common agreement between the investigators and will respect the international recommendations: "Uniforms Requirements for Manuscripts Submitted to Biomedical Journals" (<http://www.cma.ca/publications/mwc/uniform.htm>): notably, an authorship will be proposed to each clinical center participating in the study and to each member of the steering committee according to his/her actual participation.

Organization and responsibility

The Research Committee is responsible for developing study protocol, auditing patient eligibility and guiding interpretation of informed consent. It is also responsible for collection of complication reports, guiding diagnosis and treatment of complications and emergency intervention for serious complications, as well as approving the content and distribution of all publications related to the study.

